## **15 FINANCING AND INSURANCE**

A separate financial agreement (Clinical Trial Agreement) will be made between the Sponsor and the Principal Investigator at each site.

The study is covered under a [REDACTED] liability insurance policy. The certificate of insurance will be provided upon request.

## 16 REPORTING AND PUBLICATION OF RESULTS

[REDACTED] as the Sponsor, has a proprietary interest in this study. Authorship and manuscript composition will reflect joint cooperation among multiple Principal Investigators and sites and [REDACTED]. Authorship will be established prior to the writing of the manuscript. As this study involves multiple sites, no individual publications will be allowed prior to completion of the final report of the multicenter study except as agreed with [REDACTED].

All information, including but not limited to information regarding RHA®4 or the Sponsor's operations supplied by the Sponsor to the Principal Investigator and not previously published, along with any data generated as a result of this study are considered confidential and remain the sole property of the Sponsor. The Principal Investigator agrees to maintain this information in confidence, and will use the information only to perform the study.

The Sponsor or its designee is responsible for preparing a clinical study report.

The Sponsor or its designee is responsible for publicly registering this study on <http://www.clinicaltrials.gov/> prior to initiating enrolment.

## 18 APPENDICES

### APPENDIX A: ADJUSTMENTS OF VISITS AND ASSESSMENTS DUE TO PUBLIC HEALTH EMERGENCY OF COVID-19

#### 1. General Guidance

Subject safety and preserving the integrity of the data are of the highest priority. Any federal, state and local rules, guidances, or laws shall be followed.

Study visits and procedures should be followed per-protocol whenever possible. Any specific changes in study conduct that deviate from the protocol should be communicated to the sponsor via reporting to the site's Clinical Research Associate (CRA), Clinical Project Manager (CPM), and IRB, as applicable. All protocol deviations which occur as a result of COVID-19 disruptions (including remote visits), will be differentiated from other deviations and must be documented on the appropriate reporting forms/source document, and clearly annotated "protocol deviations due to COVID-19 illness/restrictions/etc.". If the subject is unable or unwilling to come to the site due to COVID-19, the TI needs to ask for the reasons and document them in the source documents.

The TI is responsible for ensuring subjects' safety and for monitoring all active subjects per protocol. TI must ensure that study subjects are kept informed of changes to the study and monitoring plans that could impact them.

Should a subject develop any symptoms that could be related to COVID-19 or any other acute infection disease, the subject will be instructed to:

- Contact the TI as soon as possible
- Contact their general physician to be examined and determine the course of action according to the standard of care.

The TI or designee will follow-up with the subject as needed but at least within 72 hours of awareness to obtain an update on the subject's health and to obtain information on whether COVID-19 has been diagnosed or not. If the subject has been diagnosed with COVID-19, the event will be reported as an AE.

[REDACTED]

[REDACTED]

[REDACTED]

[REDACTED]

[REDACTED]

[REDACTED]

[REDACTED]

[REDACTED]

[REDACTED]

[REDACTED]

[REDACTED]

[REDACTED]

[REDACTED]

1. INTRODUCTION

This statistical analysis plan (SAP) gives a comprehensive and detailed description of statistical techniques to be used for [REDACTED]. The purpose of this SAP is to ensure the credibility of the study findings by pre-specifying the statistical approaches for the analysis of study data prior to database lock. This SAP provides additional details concerning the statistical analyses outlined in the protocol. Whenever differences exist in descriptions or explanations provided in the protocol and SAP, the SAP prevails.

The structure and content of this SAP provides sufficient detail to meet the requirements identified by the Food and Drug Administration (FDA) and International Conference on Harmonisation (ICH) of Technical Requirements for Registration of Pharmaceuticals for Human Use: Guidance on Statistical Principles in Clinical Trials. All work planned and reported for this SAP will follow internationally accepted guidelines, published by the American Statistical Association and the Royal Statistical Society, for statistical practice.

The planned analyses identified in this SAP may be included in clinical study reports (CSRs), regulatory submissions, or future manuscripts. Also, post-hoc analyses not identified in this SAP may be performed to further examine study data. Any post hoc or unplanned analysis performed will be clearly identified as such in the final CSR.

1.1 Background

Hyaluronic acid (HA) is a long-chain, repeated dimer, N-acetyl glucosamine and D-glucuronic acid polymer and is a major component of the extracellular matrix. Due to its natural viscoelastic and hydrogel properties, HA is widely used as matrix in tissue regeneration and particularly in dermal defect reconstruction.

RHA® [REDACTED] dermal filler is a device containing colorless, biodegradable, sterile, biocompatible, crosslinked HA of non-animal origin (i.e., bacterial fermentation using *Streptococcus zooepidemicus*). Crosslinking is performed using 1,4-butanediol diglycidyl ether (BDDE) to form a gel. RHA® [REDACTED] contains 0.3% w/w of lidocaine hydrochloride, a drug substance widely used for its anesthetic properties (i.e., it blocks the origin and transmission of nervous influx at the point of injection by stabilizing the neuronal membrane).

[REDACTED]

[REDACTED]

1.2 Rationale for Study

[REDACTED]

[REDACTED]

1.3 Hypothesis

RHA® [REDACTED] injected in NLFs with a small cannula is non-inferior to RHA® [REDACTED] injected in the NLFs with a needle for the correction of moderate to severe NLFs as determined by the NLF-WSRS (validated NLF Wrinkle Severity Rating Scale) at [REDACTED] from last treatment.

A change from Baseline in the NLF-WSRS of ≥ 1 -grade will be considered clinically meaningful, and the non-inferiority margin for change in NLF-WSRS between needle and cannula will be 0.5 grade. The formal hypothesis set to be tested is as follows:

$$H_0: \mu_{\Delta(\text{needle} - \text{cannula})} \geq 0.5$$

$$H_a: \mu_{\Delta(\text{needle} - \text{cannula})} < 0.5$$

where $\mu_{\Delta(\text{needle} - \text{cannula})}$ represents the mean difference in change from Baseline between needle and cannula.

1.4 Study Objectives

The study is designed to achieve the following objectives:

1. Demonstrate the non-inferiority of RHA[®] [REDACTED] injected in the NLFs with a cannula versus the control (RHA[®] [REDACTED] injected in NLF with a needle) [REDACTED] from last treatment for the correction of moderate to severe NLFs. Assessment of non-inferiority will be based on the change from Baseline in NLF-WSRS [REDACTED] as rated by the Blinded Live Evaluator (BLE) at each investigative site.
2. Evaluate the safety of RHA[®] [REDACTED] injected in NLF with a cannula versus the control up to [REDACTED] from last treatment.

2. OVERVIEW OF STUDY DESIGN

2.1 Study Design

This is a randomized, controlled, single-blinded, within-subject (split-face), multicenter, prospective study to investigate whether RHA[®] [REDACTED] injected in NLFs with a small cannula [REDACTED] [REDACTED] is non-inferior to RHA[®] [REDACTED] injected in NLFs with a needle [REDACTED] for the correction of moderate to severe NLFs as determined by the Blinded Live Evaluator (BLE) using the NLF-WSRS (validated NLF Wrinkle Severity Rating Scale) [REDACTED] following last [REDACTED].

[REDACTED]

[REDACTED]

[REDACTED]

[REDACTED]

2.2 Study Design Rationale

2.2.1 Study Population

[REDACTED]

[figure not shown]

3. TREATMENT ALLOCATION, RANDOMIZATION AND BLINDING

[REDACTED]

[REDACTED]

[REDACTED]

[REDACTED]

4. DEVICE ADMINISTRATION

[REDACTED]

[REDACTED]

[REDACTED]

[REDACTED]

4.1 Injection of Study Devices

[REDACTED]

[REDACTED]

[REDACTED]

[REDACTED]

[REDACTED]

[REDACTED]

A large black rectangular redaction box covers the majority of the page content, starting below the header and ending above the footer. The redaction is irregular, with some white space visible at the top and bottom edges.

5. STUDY EVALUATIONS

5.1 Effectiveness Variables

A page with several horizontal black redaction bars. A large, semi-transparent 'EDIT' watermark is centered in the middle of the page. The background is white.

[REDACTED]

[REDACTED]

[REDACTED]
IE
[REDACTED]

[REDACTED]

[REDACTED]

5.2 Safety

[REDACTED]

5.2.1 Adverse Events

The Treating Investigator will assess AEs

[REDACTED]

5.2.2 Patient Common Treatment Response Diary

The study coordinator will provide subjects with instructions for daily recording of his/her observations of the CTRs of the study treatments into an electronic diary for the first 4 weeks after each treatment. The diary will be activated after treatment and will be discussed during the 3-day post-injection telephone follow-up.

[REDACTED]

[REDACTED]

[REDACTED]

[REDACTED]

[REDACTED]

[REDACTED]

[REDACTED]

A bar chart illustrating the distribution of a variable across 15 categories. The y-axis is labeled "Category" and the x-axis is labeled "Value". The bars are black with thin white outlines. The distribution is highly right-skewed, with the highest value (category 15) being significantly larger than the others.

Category	Value
1	10
2	12
3	15
4	20
5	25
6	30
7	35
8	40
9	45
10	50
11	55
12	60
13	65
14	70
15	150

6. STATISTICAL METHODS

6.1 Analysis Populations

A horizontal bar chart consisting of five black bars with white outlines. The bars are positioned in a sequence from left to right, with heights increasing in a non-linear fashion. The first bar is the shortest, followed by a medium bar, a tall bar, a medium bar, and the longest bar on the far right.

6.2 Primary Effectiveness Endpoint

The primary endpoint of NLF-WSRS change from Baseline █ as rated by the BLE will be analyzed in a non-inferiority statistical model using the PP population with a 0.5 margin for the difference between cannula and needle. A sensitivity analysis will be done using the ITT population. Expressing the difference between treatment groups as the mean of change from Baseline in RHA®█ injected with needle minus change from Baseline in RHA®█ injected with cannula, the one-sided 97.5% confidence limit must be < 0.5 to conclude non-inferiority. A paired t-test will be used to calculate the confidence interval to account for dependence. The formal hypothesis set to be tested is:

$$H_0: \mu_{\Delta(\text{needle} - \text{cannula})} \geq 0.5$$

$$H_a: \mu_{\Delta(\text{needle} - \text{cannula})} < 0.5$$

[figure not shown]
[figure not shown]
[figure not shown]
where $\mu_{\Delta(\text{needle} - \text{cannula})}$ represents the mean difference in change from Baseline between needle and cannula.

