### **3 COMPLIANCE STATEMENT**

The study will be conducted in accordance with the protocol, International Conference on Harmonization (ICH) and Good Clinical Practice (GCP), the Declaration of Helsinki, and the United States (US) Code of Federal Regulations (CFR) applicable to clinical studies (45 CFR Part 46, 21 CFR Part 50, 21 CFR Part 56, and 21 CFR Part 312). In addition, the study will be conducted in compliance with all applicable laws and regulatory requirements relevant to the use of new medical devices in the United States.

The sites' Principal Investigator (also referred to as the Treating Investigator [TI], both terms are used interchangeably) is responsible for ensuring the privacy, safety and welfare of the subjects during and after the study, and must ensure that personnel are trained and immediately available in case of a medical emergency. The TI must be familiar with the background and requirements of the study and with the properties of the study device as described in the Investigator's Brochure and package inserts. The Principal Investigator at each site has the overall responsibility for the conduct and administration of the study at their site, and for contact with study site management, and local authorities. [REDACTED] will facilitate and manage all interactions between the site and the IRB.

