#### 9.2.3 Visit 2 (██████████)

- Concomitant medications/treatments
- Adverse Event evaluation (including CTR Diary review)

- Photography (if T/U, taken pre-treatment)

- TI Assessments

- Subject Assessments

- Touch-up Injections (TI discretion)

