### 10.2 Withdrawal

A subject will be withdrawn from the study for any of the following reasons:

- Lost to follow-up;
- Withdrawal of consent;
- The Principal Investigator believes that for safety reasons (e.g., AE, concurrent illness) that it is in the best interests of the subject to be withdrawn from study participation;
- The subject's attending physician requests that the subject be withdrawn from the study;
- The Principal Investigator or the Sponsor, for any reason, stops the study or stops the subject's participation in the study.

Protocol deviations will not lead to automatic withdrawal unless they indicate a significant risk to the subject's safety. All major protocol deviations must be discussed promptly with the Medical Monitor.

A subject may be withdrawn from the study, in consultation with the Medical Monitor, for any of the following reasons:

- Lack of compliance to study procedures;
- A major protocol deviation or violation;
- Poor visit attendance.

Should a subject decide to withdraw after administration of a study device(s), or should the Principal Investigator decide to withdraw the subject, the Principal Investigator (or designate) will complete and report the observations up to the time of withdrawal.

All subjects who are withdrawn from the study will be requested to come in to complete their next scheduled clinic visit. The next scheduled visit may be brought forward to facilitate this. A complete evaluation at the time of the subject's withdrawal should be made. Additionally, subjects who withdraw from the study will be requested to allow continued safety monitoring, either via telephone interviews or clinic visits, whichever is more appropriate.

The reason and date of withdrawal must be noted on the eCRF. If the reason for withdrawal is an AE or an abnormal laboratory test result, monitoring will continue until resolution or until an appropriate medical judgment concerning the cause or importance has been made. The specific event or test result(s) must be recorded on the eCRF.

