#### 11.4 Analysis Populations

Three subject analysis populations are defined: Intent-to-Treat (ITT) Population, Per Protocol (PP) Population, and Safety (SAFT) Population. All analysis populations will be defined and determined prior to database closure and unblinding for the final analysis.

[REDACTED]

[REDACTED]

[REDACTED]

[REDACTED]

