## 11.7 Effectiveness Analysis

### 11.7.1 Primary Endpoint

The primary endpoint of NLF-WSRS change from Baseline [REDACTED] as rated by the BLE will be analyzed in a non-inferiority statistical model using the PP population with a 0.5 margin for the difference between cannula and needle.

[REDACTED]

[REDACTED]

[REDACTED]

[REDACTED]

[REDACTED]

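### Should the ITT result also have to pass before non-inferiority is claimed, rather than serve only as a sensitivity analysis?

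*SAP*

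**What the plan says.** Protocol 11.7.1 states that the primary endpoint, change from Baseline in NLF-WSRS rated by the Blinded Live Evaluator (BLE), "will be analyzed in a non-inferiority statistical model using the PP population with a 0.5 margin for the difference between cannula and needle". SAP 6.2 repeats this and continues: "A sensitivity analysis will be done using the ITT population". The difference is needle minus cannula, its interval comes from a paired t-test, and "the one-sided 97.5% confidence limit must be < 0.5 to conclude non-inferiority". That last sentence names no population. PP is the natural reading because it is the primary analysis, but this is an inference.

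Protocol 11.4 names three populations (ITT, PP, safety) and says that "All analysis populations will be defined and determined prior to database closure and unblinding for the final analysis". The PP and ITT definitions, the missing-data rule and the sample-size basis are blacked out, as is most of what follows the PP sentence in protocol 11.7.1. Where the documents differ, SAP section 1 says the SAP governs; on PP as primary they agree.

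**The concern.** PP membership can depend on what happens after randomization, and some of that is in the hands of the person who gave both injections and knows which side had the cannula. Under protocol 10.2 a subject is withdrawn if "The Principal Investigator believes that for safety reasons (e.g., AE, concurrent illness) that it is in the best interests of the subject" to leave the study, and protocol section 3 describes the Principal Investigator as "also referred to as the Treating Investigator [TI], both terms are used interchangeably". Touch-up at Visit 2 is also at that investigator's discretion (protocol 9.2.3).

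Each subject contributes both sides, so an exclusion removes a pair. Bias arises only if exclusion is linked to the needle-cannula difference. If subjects with a poor cannula side were the ones dropped, the PP limit could fall below 0.5 while the mean over all randomized subjects sat at the margin, and a failed ITT analysis would carry no stated consequence. In a pivotal study that would put the main claim in doubt.

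**Working it through.** The plan gives no figure to reproduce: SD, expected difference, power and expected exclusions are not visible. From the documents: at least 50 subjects (protocol 4.2.1), margin 0.5, one-sided 97.5% limit, paired t. Assumed: normal differences, SD 0.6 / 0.8 / 1.0 (0.75 in step 1), *k* subjects outside PP but with a BLE score, and their mean deficit *d*. A positive difference favours the needle.

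**1. Can the two analyses disagree?** Upper limit = mean + t(0.975, n−1) × SD/√n.
- PP, n = 45, mean 0.25, SD 0.75: 0.25 + 2.015 × 0.75/√45 = 0.475, pass.
- Add 5 subjects at 1.0 grade. ITT mean = (45 × 0.25 + 5 × 1.0)/50 = 0.325. Sum of squares = 44 × 0.5625 + 45 × 0.075² + 5 × 0.675² = 27.28, so SD = √(27.28/49) = 0.746. Limit = 0.325 + 2.010 × 0.746/√50 = 0.537, fail.
- With a PP mean of 0.20 instead, the limits are 0.425 and 0.493, and both pass.

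Disagreement is possible but needs a PP result already near the margin.

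**2. How often would PP alone pass with the overall mean at 0.5?** The PP mean is then m = (25 − k·d)/(50 − k). With n = 50 − k, the probability of passing is P(T < −t(0.975, n−1)), where T is noncentral t with n−1 degrees of freedom and noncentrality (m − 0.5)√n/SD. For k = 5, d = 1.0, SD 0.8: m = 20/45 = 0.444, noncentrality = −0.0556 × 6.708/0.8 = −0.466, probability 6.6%.

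| Mean deficit of excluded | 2 excluded (SD 0.6 / 0.8 / 1.0) | 5 excluded (SD 0.6 / 0.8 / 1.0) |
|---|---|---|
| 0.5 (uninformative) | 2.5 / 2.5 / 2.5% | 2.5 / 2.5 / 2.5% |
| 0.6 | 2.8 / 2.7 / 2.7% | 3.3 / 3.1 / 3.0% |
| 0.75 | 3.3 / 3.1 / 2.9% | 4.9 / 4.2 / 3.8% |
| 1.0 | 4.2 / 3.7 / 3.4% | 8.8 / 6.6 / 5.5% |

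Requiring ITT as well brings the last row to about 2.0 to 2.2%, largely by construction, because the ITT mean was set at the margin. These are errors only with respect to all randomized subjects. In the worst row the PP mean is itself inside the margin, at 0.444.

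**3. What would a joint rule cost?** Simulation, 200,000 trials per setting, success with PP alone → with both.
- Uninformative exclusions, 5 of 50: loss 0.0 / 0.1 / 0.8 points at a true difference of 0, and 0.8 / 2.5 / 3.3 points at 0.2.
- 5 excluded at 1.0, the rest at 0.2, overall mean (45 × 0.2 + 5 × 1.0)/50 = 0.28: 90.7 → 66.3%, 69.1 → 43.9%, 50.3 → 30.6%, a loss of 24 / 25 / 20 points.
- 2 excluded at 1.0, the rest at 0.2, overall mean (48 × 0.2 + 2 × 1.0)/50 = 0.232: 92.4 → 85.6%, 72.1 → 62.2%, 52.8 → 44.0%, a loss of 7 / 10 / 9 points.

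**4. Would the joint rule reach the routes named?** Touch-up is part of the planned treatment: the endpoint is timed from the last treatment, initial or touch-up (protocol Synopsis; SAP 2.2.2), and no visible text makes touch-up a ground for PP exclusion. A safety withdrawal may leave no BLE score at the primary time point, and ITT then adds nothing unless the hidden missing-data rule supplies a value. If only 2 of the 5 excluded have a score (d = 1.0), requiring both still leaves 4.9 / 4.1 / 3.7%; if none has, there is no gain. The subjects it does reach are those excluded but scored, such as subjects kept in the study after a deviation. For them the documents give no reason why exclusion should follow a cannula deficit.

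**The case for a change.** The strongest case for a change is that exclusion can track outcome without bad faith, that the consequence of a PP/ITT disagreement is best settled before results are known, and that one SAP sentence would do it because the ITT analysis is already planned. Excluded subjects will often have scores, since neither deviations nor prohibited therapy lead automatically to withdrawal (protocol 10.2 and 7.5). The large power losses arise only when the excluded subjects did markedly worse with the cannula, which is when PP represents the randomized subjects least well.

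Part of this stands: no visible text says how a disagreement would be read, and PP alone can exceed 2.5% in the way shown. But the scenario is assumed, and the top figure of 8.8% needs 5 exclusions, the smallest SD and a deficit of twice the margin. The power loss falls on a product whose true mean difference is inside the margin in both populations. Nor is the change a clerical edit: it alters the success rule of a pivotal study, and aligning the protocol needs prior FDA and IRB approval (protocol 3.1).

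**Conclusion.** No change follows. Testing non-inferiority in PP is a recognised choice, because deviations that blur the two sides can pull an ITT difference towards zero; ITT is not automatically the stricter test. Protocol and SAP agree on PP, a blinded evaluator scores the endpoint, populations are fixed before unblinding, and the Medical Monitor is consulted on withdrawals for deviations.

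The excess over 2.5% is 0.2 to 1.7 points with 2 excluded and 0.5 to 6.3 points with 5, given SDs of 0.6 to 1.0, deficits of 0.6 to 1.0 grade and an overall mean exactly at the margin. It is zero if exclusions are unrelated to the difference. Against that, a joint rule costs up to about 25 points of success when the product is within the margin, so it is a trade-off on which statisticians would differ. What remains is a detail of interpretation that hidden text may already supply. With both analyses planned, a statistician would report both limits together and discuss any disagreement.

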6.3 Secondary Effectiveness Endpoints

All statistical inference tests will be performed at the same significance level (α) of 0.05. For categorical and continuous variables, the two groups will be compared using two-sided parametric or non-parametric tests for paired data, as appropriate. For continuous variables, the Shapiro-Wilk test will be used to assess normality. If data are normally distributed, testing will be conducted using the Student t-test, while testing will be conducted with the Wilcoxon signed-rank test if not normally distributed.

6.4 Safety Endpoints

The SAFT Population will be used to summarize the safety of the study devices and will consist of all treated subjects. The primary safety analysis is the calculation of the incidence of CTRs and adverse events in the study period. Point estimates for all CTRs, AEs and SAEs will be presented and two-sided exact 95% confidence intervals will be calculated for the overall incidence of AEs and SAEs. Tables will be generated which summarize AEs by investigator assessments of both relationship to treatment and severity.

